7.9.1.1 Analysis Methods

Analyses of PD-L1 will include:

- Examine the distribution of TPS and CPS
- Assess potential associations between TPS or CPS and efficacy measures

7.9.1.2 Distribution of PD-L1 Expression

Descriptive statistics of PD-L1 expression and PD-L1 status (for both TPS and CPS) will include:

- Listing of all PD-L1 IHC data using all PD-L1 tested subjects.
- Summary of tumor specimen acquisition and characteristics using all treated and PD-L1 tested subjects.
- Summary statistics of PD-L1 expression by tumor type using all treated and PD-L1 tested subjects.
- Waterfall plot of PD-L1 expression at baseline by tumor type using all treated and PD-L1 tested subjects.
- Frequency of PD-L1 expression status by tumor type using all treated and PD-L1 tested subjects, including indeterminate and not evaluable if over 5% of subjects in the population fall in this category.

7.9.1.3 Association Between PD-L1 Expression and Efficacy Measures

Analyses will be performed using all treated and PD-L1 tested subjects, if not otherwise specified, for the followings:

- BOR, PFS, OS, DOR and pCR will be summarized using frequency and percentage for each tumor type, by baseline PD-L1 status (both TPS and CPS). Objective response rate and pathologic complete response rate, with exact 95% CIs will be computed using the Clopper-Pearson method.
- Box plots of PD-L1 expression versus response status will be generated for each tumor type using all PD-L1 evaluable subjects.
- Waterfall plot of best reduction from baseline target lesion will be generated for each tumor type by PD-L1 status (both TPS and CPS) at baseline using all PD-L1 evaluable subjects.

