7 STATISTICAL ANALYSES

7.1 General Methods

Unless otherwise noted, the following subsections describe tabulations of discrete variables, by the frequency and proportion of subjects falling into each category. Percentages given in these tables will be rounded and, therefore, may not always sum to 100%. Continuous variables will be summarized using the mean, standard deviation, median, minimum and maximum values. If a missing category is not being presented in the data display, only those subjects with non-missing values for the parameter being assessed are included in the percentage calculation.

Time to event distribution (e.g. progression free survival, overall survival, time to response, and duration of response) will be estimated using Kaplan Meier techniques. When appropriate, the median along with the corresponding log-log transformed 95% CI will be estimated. Rates at fixed time points will be derived from the Kaplan Meier estimate and corresponding confidence intervals will be derived based on Greenwood formula³ for variance derivation and on log-log transformation applied on the survivor function $S(t)$ ⁴.

Confidence intervals for binomial proportions will be derived using the Clopper-Pearson method⁵.

All analyses will be performed separately for each tumor type upon completion of follow-up for the primary endpoint in each tumor type. Safety analyses will also be performed for each tumor type.

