7.5.2 Secondary Analyses (Metastatic Cohorts Only)

7.5.2.1 Duration of Response Based on Investigator Assessment

DOR will be summarized for subjects who achieve confirmed PR or CR using the Kaplan-Meier product-limit method. Median values of DOR, along with two-sided 95% CI using the log-log transformation will also be calculated by cohort. In addition, the percentage of responders still in response at different time points (3, 6, and 12 months) will be presented based on the KM plot.

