7.5.2.3 Overall Survival

OS curves for each tumor type will be estimated using the Kaplan-Meier (KM) product limit method. Median OS and the corresponding two-sided 95% confidence intervals using the log-log transformation will be computed. Survival rates at 3, 6, 12, 18, 24, 36, 48, and 60 months will be estimated using KM estimates on the OS curve for each tumor type. Minimum follow-up must be longer than the time point to generate the rate. Associated two-sided 95% CIs will be calculated.

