7.5.2.4 Progression Free Survival

PFS curves for each tumor type will be estimated using the Kaplan-Meier (KM) product limit method. Median PFS and the corresponding two-sided 95% confidence intervals using the log-log transformation will be computed. Survival rates at 3, 6, 9, 12 months will be estimated using KM estimates on the PFS curve for each tumor type. Minimum follow-up must be longer than the time point to generate the rate. Associated two-sided 95% CIs will be calculated.

The source of progression (death vs. progression) will be summarized.

The status of subjects who are censored in the PFS Kaplan-Meier analysis will be tabulated using following categories:

- Still on-treatment
- Received subsequent anti-cancer therapy (stem cell transplant, other)
- Progression-free in follow-up
- Off-study (lost to follow-up, withdrew consent, other).

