7.9.2.1 Association Between Virus Status and Efficacy Measures

- BOR, PFS, OS, DOR and pCR will be summarized using frequency and percentage for each tumor type, by virus status. Objective response rate and pathologic complete response rate, with exact 95% CIs will be computed using the Clopper-Pearson method.
- Waterfall plot of best reduction from baseline target lesion will be generated for each tumor type by virus status.

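### SAP 7.9.1.3 and 7.9.2.1 assign counts and percentages to PFS, OS and DOR by PD-L1 and virus status, in conflict with the Kaplan-Meier rule in SAP 7.1

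*SAP*

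**What the plan says.** SAP 7.9.1.3 (PD-L1): "BOR, PFS, OS, DOR and pCR will be summarized using frequency and percentage for each tumor type, by baseline PD-L1 status". SAP 7.9.2.1 (virus status): "BOR, PFS, OS, DOR and pCR will be summarized using frequency and percentage for each tumor type, by virus status". After that sentence, each section adds an interval method only for the objective response rate and the pathologic complete response rate (Clopper-Pearson). Neither mentions Kaplan-Meier curves, medians or fixed-time rates.

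SAP 7.1 gives a general rule for the same endpoints: "Time to event distribution (e.g. progression free survival, overall survival, time to response, and duration of response) will be estimated using Kaplan Meier techniques". It adds medians with log-log intervals, and "Rates at fixed time points will be derived from the Kaplan Meier estimate".

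The secondary-analysis sections follow that rule:
- SAP 7.5.2.1: "DOR will be summarized for subjects who achieve confirmed PR or CR using the Kaplan-Meier product-limit method".
- SAP 7.5.2.3: "OS curves for each tumor type will be estimated using the Kaplan-Meier (KM) product limit method".
- SAP 7.5.2.4: "PFS curves for each tumor type will be estimated using the Kaplan-Meier (KM) product limit method".

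These three sections work by cohort or tumor type, not by PD-L1 or virus status. The subgroup list in SAP 7.5.1.2 applies to ORR only.

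**The concern.** BOR and pCR are categorical, so counts and percentages suit them. PFS, OS and DOR are not. Under SAP 4.2.1, OS is censored at the last date known alive and DOR at the last evaluable assessment. PFS is censored at the last assessment, or at the last assessment before new anticancer therapy. A raw percentage with an event counts a subject censored early in the same way as one followed event-free for years.

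Section 7.9 is the only place in the SAP that says how these endpoints are summarized by PD-L1 or virus status. A programmer working from it could produce event counts and stop there. A reader of the report could then take a gap in those percentages for a biomarker association when it partly reflects length of observation.

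**Working it through.** No figure in the plan is at issue, so there is nothing to reproduce. The check has two parts.

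**1. The sections side by side**

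| Endpoint | General rule (SAP 7.1) | By cohort or tumor type | By PD-L1 or virus status (SAP 7.9.1.3, 7.9.2.1) |
|---|---|---|---|
| BOR/ORR, pCR | Frequencies; Clopper-Pearson | The same | Frequencies; Clopper-Pearson |
| PFS, OS, DOR | Kaplan-Meier | Kaplan-Meier (7.5.2.1, 7.5.2.3, 7.5.2.4) | Counts and percentages only |

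The bottom right cell is the only one out of line. SAP 7.1 does not restrict its Kaplan-Meier rule to the overall population, and section 7.9 does not say that it departs from it. The SAP has no rule on which section prevails.

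**2. What a crude percentage would do (all inputs assumed)**

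The documents give no survival or follow-up by subgroup. Take exponential survival, identical in two subgroups, with median m. If every subject is followed for F months, the expected proportion with an event is 1 − exp(−ln 2 × F/m). With m = 12:
- F = 12: 1 − exp(−ln 2 × 12/12) = 50.0%.
- F = 18: 1 − exp(−ln 2 × 18/12) = 64.6%.
- Difference: 14.6 points with no true effect.

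Now let follow-up vary uniformly from a to b months. The expected crude proportion is 1 − (e^(−λa) − e^(−λb)) / (λ(b − a)), with λ = ln 2/m. A simulation (20 subjects per subgroup, 2,000 runs) adds the Kaplan-Meier event rate at 12 months.

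| Median (months) | Follow-up (months) | Crude %, formula | Crude %, simulated | KM 12-month %, simulated | True 12-month % |
|---|---|---|---|---|---|
| 12 | 12–18 | 57.7 | 58.2 | 50.5 | 50.0 |
| 12 | 24–36 | 82.0 | 82.1 | 50.3 | 50.0 |
| 20 | 12–18 | 40.4 | 40.7 | 34.2 | 34.0 |
| 20 | 24–36 | 64.4 | 64.1 | 34.1 | 34.0 |

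The simulated crude gaps are 82.1 − 58.2 = 23.9 points and 64.1 − 40.7 = 23.4 points. The Kaplan-Meier rates agree within 1 point.

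Two limits apply. If both subgroups have the same follow-up, administrative censoring alone produces no gap. Also, nobody in this set-up is censored before month 12, so the Kaplan-Meier value there equals the simple proportion at a fixed time. The Kaplan-Meier method itself is needed once subjects are censored before the chosen time, as the PFS rule on new therapy allows.

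**The case against.** The strongest reply is that SAP 7.1 already settles the matter. It names PFS, OS and DOR, prescribes Kaplan-Meier and is not confined to the whole population. Its opening exception clause attaches to the sentence on tabulating discrete variables, not to the Kaplan-Meier sentence. The matching wording in 7.9.1.3 and 7.9.2.1 may simply be reused text. Event counts can also sit beside Kaplan-Meier estimates: SAP 7.5.2.4 plans both for PFS. SAP section 9 leaves table layouts to a Data Presentation Plan that is not among the documents.

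Much of this stands. A reader might infer that these analyses will ignore censoring. The text does not establish that, because the general rule and the subgroup wording point different ways and neither is said to prevail. What the reply does not remove is that the only sections dealing with these subgroup summaries name a method that does not fit three of the five endpoints listed.

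A reader might also take these for the trial's main biomarker comparisons. The study is non-comparative by title. SAP 3.3 lists the biomarker associations as exploratory, and the SAP specifies no test or decision rule for PFS, OS or DOR by subgroup. Protocol 8.4.5 mentions Fisher's exact test, or another suitable method, for PD-L1 and efficacy measures in general, without naming these endpoints. PD-L1 and virus status are prominent only in that SAP 7.9 sends all other biomarkers to a separate SAP.

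Finally, some virus-negative groups may be too small for medians under any method. Protocol 3.3.1 excludes subjects already known to be virus-negative from several metastatic tumor types, and Protocol 1.1.1.2 puts HPV infection in cervical cancer at nearly 100%. That limits what the fix can require.

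**Conclusion.** The point holds as an inconsistency and an unsuitable stated summary. SAP 7.9.1.3 and 7.9.2.1 prescribe counts and percentages for endpoints that SAP 4.2.1 defines with censoring and SAP 7.1 assigns to Kaplan-Meier. Followed to the letter, they give event percentages that vary with follow-up.

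The size for this trial is unknown. The 14.6-point example needs exponential survival, a 12-month median and follow-up of 12 versus 18 months, all assumed. The gaps of about 23 to 24 points need a larger assumed imbalance. It is tempting to read either as the bias to expect here, but the documents do not support that. The Schedule of Analyses in SAP section 1 times the primary analysis at one year after the last subject's first dose, so earlier subjects are followed longer. Nothing shows that PD-L1 or virus status tracks enrolment time within a tumor type.

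The ORR analysis and the main PFS, OS and DOR analyses are unaffected. The consequence is confined to exploratory, descriptive tables, where the correction is still worth making because the text gives the wrong instruction twice.

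**What to change.** In SAP 7.9.1.3 and 7.9.2.1:
- Limit counts and percentages, as the method of summary, to BOR and pCR, keeping the Clopper-Pearson intervals for ORR and pCR rate.
- State that PFS, OS and DOR by PD-L1 status and by virus status use the Kaplan-Meier methods of SAP 7.1 and 7.5.2: curves, medians with log-log 95% CIs where estimable, and fixed-time rates where subgroup size and follow-up allow. SAP 7.5.2.3 and 7.5.2.4 already require minimum follow-up to exceed the time point, and that condition can be carried over.
- Allow event counts to be shown beside the Kaplan-Meier estimates.

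The cost is a change of wording in two SAP sections and a matching check of the table layouts. No new data or method is needed, since the SAP already specifies Kaplan-Meier estimation for these endpoints.

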7.9.2 Virus Status

- The following virus status subgroups will be considered by tumor type for cohorts (N-3) GYN (Cervical, vaginal, and vulva) Carcinoma, (N-4) Merkel Cell Carcinoma, (M-3) GYN (Cervical, vaginal, and vulva) Carcinoma, (MC-2a, MC-2b, MC-exp) Cervical Carcinoma, (MC-3a, MC-3b) anogenital HPV associated tumors (vaginal/vulvar/anal canal/penile), (M-4, MC-4a) Merkel Cell Carcinoma and (M-5, MC-5a) Nasopharyngeal Carcinoma (NPC), for which the virus status are tested retrospectively. .
- Virus status tested
 - Virus positive

- Virus negative
- Virus status not tested

7.9.2.1 Association Between Virus Status and Efficacy Measures

- BOR, PFS, OS, DOR and pCR will be summarized using frequency and percentage for each tumor type, by virus status. Objective response rate and pathologic complete response rate, with exact 95% CIs will be computed using the Clopper-Pearson method.
- Waterfall plot of best reduction from baseline target lesion will be generated for each tumor type by virus status.

7.10 Outcome Research Analyses

7.10.1 EORTC-QLQ-C30

Unless otherwise specified, the analysis of EORTC QLQ C-30 will be performed in all treated subjects who have an assessment at baseline and at least one subsequent assessment. Analyses will be performed by tumor type.

Baseline measures will be summarized using descriptive statistics (n, mean, standard deviation, 95% confidence intervals, median, first and third quartiles, minimum, maximum) for each scale, based on subjects with a baseline measurement.

Change from baseline will be summarized using descriptive statistics (n, mean, standard deviation, 95% confidence intervals, median, first and third quartiles, minimum, maximum) for each scale at each assessment time point. In addition, the percentage of subjects demonstrating a clinically meaningful deterioration (defined as a 10-point change from baseline) will be presented for each scale at each assessment timepoint. Percentages will be based on number subjects assessed at baseline and at assessment time point.

For all assessment timepoints, mean scores and mean score changes from baseline (n, mean, standard deviation, 95% confidence intervals, median, 25th and 75th percentiles, minimum, maximum) will be reported.

EORTC-QLQ-C30 questionnaire completion rate is defined as the proportion of subjects who answered the questionnaires out of number subjects assessed at assessment time point. Completion rate will be calculated and summarized for each assessment time point.

A by subject listing of QLQ-C30 with each QLQ-C30 item, functional scales, symptoms scales and global health status will be provided.

7.10.2 EuroQol EQ-5D

Unless otherwise specified, the analysis of EQ-5D⁷ will be performed in all treated subjects who have an assessment at baseline and at least one subsequent assessment. Analyses will be performed by tumor type.

Subject's overall health state on a visual analog scale (EQ-VAS) and EQ-5D index using UK weighting algorithm at each assessment time point will be summarized using descriptive statistics

(n, mean, standard deviation, 95% confidence intervals, median, 25th and 75th percentiles, minimum, maximum).

Proportion of subjects reporting problems for the 5 EQ-5D dimensions at each assessment time point will be summarized by level of problem. Percentages will be based on number subjects assessed at assessment time point.

For all assessment timepoints, mean scores and mean score changes from baseline (n, mean, standard deviation, 95% confidence intervals, median, 25th and 75th percentiles, minimum, maximum) will be reported.

A by-subject listing of EQ-5D with the problem levels for each of the 5 dimensions (mobility, self-care, usual activities, pain/discomfort and anxiety/depression), health state (5 dimensions digits combined in a 5-digit number), EQ-5D index using UK weighting algorithm and EQ-VAS will be provided.

More results of EQ-5D-Index will be presented separately and will be described in the WWHEOR SAP.

7.11 End of Study Analyses at Study Closure

Subjects who remaining on study treatment following primary analysis will be followed for safety as defined in the protocol. The end of study analyses will be performed for the selected safety data and the duration of treatment using all enrolled subjects.

The following data will be reported:

- Subject disposition
- Duration of treatment
- Death
- Adverse events
- Serious adverse events

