3.1.1 Viral Status Determination Prior to Entry

The study will enroll prospective subjects diagnosed with gastric cancer in the Metastatic Monotherapy Cohort. Gastric subjects will provide pre-screening informed consent for determination of EBV+ viral status during the screening period and be registered in IRT. Viral testing will be performed locally or by a central laboratory and test results will be collected. After positive test result confirmation, consent for demographic and further eligibility will be collected. Subjects with EBV negative gastric cancer will be considered screen failures and will not be eligible for the study.

The study will enroll prospective subjects diagnosed with SCCHN. SCCHN subjects will provide consent, via pre-screening informed consent, for determination of HPV viral status, if prior results are not available during the screening period and be registered in IRT (Combo A and C). Viral testing will be performed locally or by a central laboratory and test results will be collected. After viral test result is confirmed positive, consent for demographic and further eligibility will be collected. If subjects decline pre-screening informed consent or are unwilling to undergo viral testing, they are eligible to enroll in Combo D. However, viral status should be determined retrospectively.

The requirement for viral status for each tumor type by cohort is described below and in [Table 3.1.1-1](#).

Neoadjuvant cohort: Confirmation of viral status is required prior to study drug assignment for SCCHN subjects enrolled. Viral testing determined more than 35 days prior to first dose may be used. For SCCHN tumor types in the neoadjuvant cohort, 21 evaluable subjects with virus positive disease and 21 evaluable subjects with virus negative disease will be enrolled. No prior screening for Gyn (cervical, vaginal, vulvar) or MCC cohorts is necessary due to the high prevalence of viral positivity and the technical aspects of the MCPyV assay. Viral positivity will be tested retrospectively for MCC and Gyn tumor types.

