8.4.2.2 Secondary Endpoints Methods

Metastatic cohort (monotherapy and combination therapies):

- Time to event distribution will be estimated using Kaplan Meier techniques. This will be done for PFS (based on investigator assessments) and OS. Median PFS or OS along with 95% CI will be constructed based on a log-log transformed CI for the survivor function. Rates at some fixed time points will be derived from the Kaplan Meier estimate and corresponding

confidence interval will be derived based on Greenwood formula for variance derivation and on log-log transformation applied on the survivor function.

- The DOR will be summarized for all treated subjects who achieve confirmed PR or CR using the Kaplan-Meier (KM) product-limit method. Median values of DOR, along with two-sided 95% CI using Brookmeyer and Crowley method, will also be calculated.

8.4.2.3 *Exploratory Endpoints Methods*

Methods for exploratory endpoints will be discussed in detail in the statistical analysis plan.

8.4.3 *Safety Analyses*

Safety analyses will be performed in all treated subjects. Descriptive statistics of safety will be presented using NCI CTCAE version 4. All on-study AEs, drug-related, AEs, SAEs and drug-related SAEs will be tabulated using worst grade per NCI CTCAE version 4 criteria by system organ class and MedDRA preferred term. On-study lab parameters including hematology, chemistry, liver function, thyroid function, and renal function will be summarized using worst grade per NCI CTCAE version 4 criteria.

The proportion of subjects in the neoadjuvant cohort with surgery delayed > 4 weeks due to a drug-related AE will be reported for each tumor type and the Clopper-Pearson method will be used to estimate the two-sided 95% confidence interval.

8.4.4 *Pharmacokinetic Analyses*

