6.3.2 Analysis Populations

Within each tumor type in each cohort the following populations will be defined.

- **Enrolled subjects:** All subjects who signed an informed consent form and were registered into the IVRS.

- **Treated subjects:** All subjects who received at least one dose of nivolumab. This is the primary population for efficacy and safety analyses.
- **Response evaluable subjects:** All treated subjects who have a BOR of CR, PR, SD, Non-CR/Non-PD or PD, and target lesion(s) assessed at baseline, and one of the following: i) at least one on-study timepoint (before sub-sequent therapy) with all baseline target lesion(s) assessed; ii) clinical progression or death before any on-study tumor assesment.
- **Evaluable neoadjuvant subjects:** All treated subjects in neoadjuvant cohorts (N-1, N-2, N-3, N-4) who have available paired tissue samples at screening and Day 29.
- **Pathologic response evaluable subjects:** All treated subject in neoadjuvant cohorts who received study treatment surgery and have known pathological response based on Day 29 TN classification.
- **Outcomes research subjects:** All treated subjects who have an assessment at baseline and at least one post baseline assessment.
- **Pharmacokinetic subjects:** All treated subjects have available serum concentration data.
- **Immunogenicity subjects:** All treated subjects with baseline and at least 1 post baseline immunogenicity assessment.
- **PD-L1 tested subjects:** All subjects who had a tumor tissue sample available for assessment of PD-L1 expression at baseline.
- **Treated PD-L1 tested subjects:** All PD-L1 tested subjects who received at least one dose of study treatment.
- **PD-L1 evaluable subjects:** All treated PD-L1 tested subjects with quantifiable PD-L1 expression.

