7.3 Study Population

7.3.1 Subject Disposition

The total number of subjects enrolled (treated or not) will be presented along with the reason for not being treated. This analysis will be performed on all enrolled population only.

Number of subjects who discontinued study treatment along with corresponding reason will be tabulated. Reason for discontinuation will be derived from subject status CRF page. This analysis will be performed only on all treated population.

A subject list for all treated subjects will be provided showing the subject's enrollment date, first and last dosing date, off study date and reason for going off-study.

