7.4 Extent of Exposure

The extent of exposure will be characterized according to the number of subjects exposed, and the duration of exposure. Analyses in this section will be performed on all Treated Subjects for each tumor type in different cohorts.

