7.4.1 Administration of Study Therapy

The following parameters will be summarized (descriptive statistics) by tumor type:

- Number (%) of treated subjects exposed for specified periods of time such as less than 1 week, 1 week to 1 month, 1 month to 6 months by treatment.
- Number of doses received (summary statistics)
- Cumulative dose
- Relative dose intensity (%) using the following categories: $< 50\%$; $50 - < 70\%$; $70 - < 90\%$; $90 - < 110\%$; $\geq 110\%$.
- Duration of treatment: duration of treatment will be presented using a Kaplan-Meier curve whereby the last dose date will be the event date for subjects who discontinued study therapy. Subjects who are still on study therapy will be censored on their last dose date. Median duration of treatment and associated 95% CI will be provided.
- A by-subject listing of dosing of study medication (record of study medication, infusion details and dose change) and a listing of batch number will be also provided.
- A by-subject listing of extent of exposure (weight, number of doses, date of first and last dose, cumulative dose, duration of treatment, and reason for discontinuation) will be provided.

Table 7.4.1-1: Administration of study therapy: definition of parameters
Nivolumab monotherapy

Nivolumab	
Dosing schedule per protocol	240 mg every 2 weeks
Cumulative Dose	Cum dose (mg) is sum of the doses (mg) administered to a subject during the treatment period.
Duration of treatment	Last dose date - Start dose date +1
Relative Dose Intensity (%)	Cum dose /[(Last dose date - Start dose date + 14) x 240/14] x 100

Nivolumab combined with Ipilimumab: Combo A

	Nivolumab	Ipilimumab
Dosing Schedule per Protocol	3 mg/kg every 2 weeks	1 mg/kg every 6 weeks
Dose	Dose (mg/kg) is defined as Total Dose administered (mg)/Most recent weight (kg). Dose administered in mg at each dosing date and weight are collected on the CRF	Dose (mg/kg) is defined as Total Dose administered (mg)/Most recent weight (kg). Dose administered in mg at each dosing date and weight are collected on the CRF
Cumulative Dose	Cum Dose (mg/kg) is the sum of the doses administered to a subject.	Cum Dose (mg/kg) is the sum of the doses administered to a subject.
Relative Dose Intensity (%)	Cum dose /[(Last dose date - Start dose date + 14) x 3/14] x 100	Cum dose /[(Last dose date - Start dose date + 42) x 1/42] x 100
Duration of Treatment	Last dose date - Start dose date + 1	Last dose date - Start dose date + 1

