7.6 Safety

For all safety related analyses, refer to the Core Safety SAP⁶. Safety will be summarized for: all treated, by tumor type; all dose escalation subjects, by tumor type.

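### Closure safety and exposure tables are set on all enrolled subjects, and the SAP's treated population requires nivolumab; both depart from the protocol's any-study-drug treated set

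*SAP*

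**What the plan says.** SAP 7.11 covers study closure: "The end of study analyses will be performed for the selected safety data and the duration of treatment using all enrolled subjects". It lists disposition, duration of treatment, deaths, adverse events and serious adverse events.

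SAP 6.3.2 defines enrolled as: "All subjects who signed an informed consent form and were registered into the IVRS". SAP 7.3.1 confirms that this includes people never dosed: "The total number of subjects enrolled (treated or not) will be presented along with the reason for not being treated". Protocol 3.1.1 shows one way that they arise: "Gastric subjects will provide pre-screening informed consent for determination of EBV+ viral status during the screening period and be registered in IRT".

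Elsewhere the safety and exposure set is different. Protocol 8.4.3: "Safety analyses will be performed in all treated subjects". SAP 7.6: "Safety will be summarized for: all treated, by tumor type". SAP 7.4, on exposure: "Analyses in this section will be performed on all Treated Subjects for each tumor type in different cohorts".

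The two documents also define treated differently. SAP 6.3.2 requires at least one dose of nivolumab and makes this the primary population for efficacy and safety. Protocol 8.2 requires at least one dose of study drug, and protocol 5.3 evaluates safety in anyone given any study drug. The SAP is not consistent with itself: its treated PD-L1 tested population (6.3.2) and its metastatic on-treatment window (Table 6.1-1) both refer to study treatment.

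**The concern.** **(a) Closure population.** A never-dosed subject has no value for duration of treatment and cannot have an on-treatment AE, yet adds one to the denominator. Nonserious AEs are collected only from the start of study drug (protocol 6.2.1). SAEs are collected from consent, and for 30 days in subjects assigned but never treated (protocol 6.1.1). Closure SAE and death percentages would therefore mix two populations, with no predictable direction of shift. The closure tables would not line up with the main safety tables of the same trial.

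**(b) Treated defined by nivolumab.** In Combo D, nivolumab starts at Week 3 after daratumumab at Weeks 1 and 2 (protocol 1.5), and daratumumab is itself an investigational product there (protocol 4.1). A subject who stops before Week 3 is treated under the protocol but not under the SAP. That subject leaves the response-rate denominator and the main exposure and safety tables, yet remains in the closure tables under 7.11. Protocol 1.5 says that daratumumab infusion reactions fall mostly at the first infusion, so such subjects could carry relevant safety data.

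**Working it through.** The plan states no figure to reproduce here. The check is a comparison of definitions, followed by illustrative arithmetic. Every never-dosed share, event rate and responder count below is an assumption.

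**Which set each section uses**

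| Output | Main analysis | Closure (SAP 7.11) |
|---|---|---|
| AEs, SAEs, deaths | All treated (protocol 8.4.3, SAP 7.6) | All enrolled |
| Duration of treatment | All treated (SAP 7.4) | All enrolled |
| Disposition | Enrolled for counts and reasons not treated; treated for reasons for stopping (SAP 7.3.1) | All enrolled |

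Duration is defined in SAP 7.4.1 as "Last dose date - Start dose date +1", which needs a first and a last dose date. The protocol names no population for duration, so that conflict is within the SAP. The safety conflict is with both documents.

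**(a) On-treatment or nonserious AEs.** Let f be the never-dosed share of enrolled subjects and assume a 40% rate in treated subjects. Printed rate = 0.40 × (1 − f).

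| f | 0% | 10% | 20% | 30% |
|---|---|---|---|---|
| Printed rate | 40% | 36% | 32% | 28% |

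**(a) SAEs.** Assume 20% in treated subjects and a rate u in the never-dosed. Printed rate = 0.20 × (1 − f) + u × f.

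| f | u = 0% | u = 10% | u = 20% | u = 30% |
|---|---|---|---|---|
| 10% | 18% | 19% | 20% | 21% |
| 20% | 16% | 18% | 20% | 22% |
| 30% | 14% | 17% | 20% | 23% |

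**(a) Gastric cohort, an extreme case.** Assume that every gastric subject was registered at pre-screening with EBV status unknown and that prevalence equals the cited 8.7% (95% CI 7.5 to 10.0; protocol 1.1.1.1). The planned 12 treated subjects then imply 12 / 0.087 ≈ 138 registered (120 at 10.0%, 160 at 7.5%). A 40% rate in the treated would print as 0.40 × 12 / 138 ≈ 3.5%.

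**(b) Combo D response rate.** The response rate divides by treated subjects (SAP 4.1.2). Let k be the number of non-responders given daratumumab only. The two-sided 95% Clopper-Pearson lower bound is shown in brackets, first for 8 responders among the planned 40, then for 4 responders among 20, since the number actually dosed is not given.

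| k | 8 of 40 − k | 4 of 20 − k |
|---|---|---|
| 0 | 20.0% (9.05%) | 20.0% (5.73%) |
| 1 | 20.5% (9.30%) | 21.1% (6.05%) |
| 2 | 21.1% (9.55%) | 22.2% (6.41%) |
| 3 | 21.6% (9.83%) | 23.5% (6.81%) |
| 4 | 22.2% (10.12%) | 25.0% (7.27%) |

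With 40 dosed, the bound passes the 10% level of clinical interest only at k = 4. With 20 dosed it never does.

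**Other cohorts.** Nivolumab is the only drug, or is infused first on Day 1 (protocol 4.3), so a nivolumab dose and a dose of any study drug select the same people.

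**The case against.** Six arguments can be made on the other side.

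- **Few subjects may be enrolled but never dosed.** SAP 2.2 describes enrolment as following consent and established eligibility. On that reading the effect of (a) is near zero. SAP 6.3.2, SAP 7.3.1 and the gastric pre-screening text point the other way. This bears on size only, and the range above includes zero.
- **The tables may be built correctly anyway.** Detailed safety methods sit in the Core Safety SAP and mock-ups in the Data Presentation Plan, neither of which is available here. SAP section 1 describes the closure work as updated safety analysis, which suggests a refresh of the main tables. That is plausible, but 7.11 names a defined population and should name the intended one.
- **Protocol 8.2 leaves the application of populations to the SAP.** Protocol 8.4.3 nevertheless fixes the safety set, and SAP 7.4 and 7.6 follow it.
- **Duration cannot be biased by subjects without a value.** This is largely right: for duration the defect is an inapplicable population, with little numerical effect.
- **SAEs and deaths in undosed subjects are legitimately collected.** This stands, and is a reason to list them separately rather than to mix them into treated-subject percentages.
- **Part (b) may affect nobody.** Combo D is closed and its combination treatment was terminated, and crossing 10% needs one particular combination of counts. This is accepted and keeps the point minor.

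**Conclusion.** Both parts hold as written. SAP 7.11 applies a population that includes never-dosed people to closure safety and exposure outputs, against protocol 8.4.3 and SAP 7.4 and 7.6. SAP 6.3.2 narrows treated to nivolumab, against protocol 8.2 and 5.3.

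Confidence is high on the text. The effect on reported results is unknown, because the documents give no count of never-dosed or daratumumab-only subjects; the latter may be zero. Severity is minor. Outside Combo D the main safety and efficacy tables are unaffected, and no sample size or other design figure changes. What is at stake is closure tables that disagree with the main ones, AE percentages too low if the enrolled number is the denominator, and a possible small upward shift in the Combo D response rate.

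**What to change.** - **SAP 7.11:** use all treated subjects for duration of treatment, deaths, AEs and SAEs. Keep all enrolled subjects for disposition only, split as in SAP 7.3.1. List SAEs and deaths in enrolled but never-treated subjects separately, so that data collected under protocol 6.1.1 still have a place.
- **SAP 6.3.2:** define treated as at least one dose of any study drug, as in protocol 8.2.

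The cost is SAP wording and the matching table specifications; dosing and status data are already collected. Relative to the text as written, closure on-treatment and nonserious AE percentages stay the same or rise, closure SAE and death percentages may move either way, and the Combo D denominator in the main tables stays the same or grows.
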